Descriptive statistics of actual value and change from baseline value in vital signs (including temperature, pulse, respiration rate, systolic blood pressure, diastolic blood pressure, and weight) will be presented by cohort group for each nominal visit and time point. However, no summaries will be presented when fewer than five patients' data are available at an assessment time point. Summaries by nominal visit will not present unscheduled visits. A vital signs listing will also be provided.

E. Electrocardiogram (ECG)

QTcF and QTcB are calculated automatically in the EDC system using the following formulae:

$$QTcF = \frac{QT}{RR^{1/3}}$$
$$QTcB = \frac{QT}{RR^{1/2}}$$

Descriptive statistics of actual value and change from baseline value in ECG parameters (including PR, RR, QRS, QT, QTcB, and QTcF) will be listed by cohort group and time

point. In addition, the summary will include descriptive statistics for the maximum postbaseline value and the minimum post-baseline value. Summaries of data for nominal time points will not include unscheduled visits; summaries of maximum and minimum postbaseline value will include unscheduled visits. The average of the triplicate ECGs at a nominal time point will be used for analysis; values will be rounded to the nearest whole number before assigning to reporting categories. If the triplicate ECGs are not available, the average of ECGs will be calculated using one or two ECGs measured at the same visit. No summaries will be presented when fewer than five patients' data are available at an assessment time point.

In addition, the number and percentage of patient experiencing the following parameters will be tabulated and summarized:

- Change (increase) from baseline in QTcF at any time during study
 - \circ >30 to \leq 60 msec
 - >60 msec
- Reaching a value in QTcF at any time during study
 - $\circ \leq 450 \text{ msec}$
 - \circ >450 to \leq 480 msec
 - \circ >480 to \leq 500 msec
 - >500 msec

A shift table summarizing the counts and percentages of patients' baseline QTcF events vs. their maximum post-baseline event will also be presented.

A subset of approximately 30 patients will be consented to 24-hour Holter ECG monitoring for the purposes of the exposure-response modeling the effect of drug exposure on QTcF interval. This model-based analysis will be described in a separate, stand-alone SAP.

A data listing of all ECG values will also be provided, which will list the triplicate values obtained for each timepoint, as well as the derived mean value for each nominal time point.

F. Physical Examination and Pregnancy Test

Physical examination findings and data for pregnancy test will be listed in a patient data listing, but not summarized. The records of abnormal findings prior to or after the first dose of study drug from physical exam will be captured in the medical history CRF and adverse events CRF, respectively.

G. Concomitant Medications

Medications will be coded using the WHO Drug Dictionary version of September 2016, with verbatim terms coded by Anatomical Therapeutic Chemical (ATC) classification and Preferred Term (PT).

To determine whether a medication is a prior or concomitant medication, the imputed nonmissing stop date of the medication is used. If this date is on or after the start of first dosing date of study drug, the medication will be defined as concomitant medication; otherwise it will be classified as prior medication.

If the medication stop date is missing, imputation rules specified for AE stop date will be applied. If the medication date is still missing after implementing the rules, the most conservative approach is taken, and the medication is considered to be concomitant.

The concomitant medications will be summarized by ATC classification and PT. For each medication term, the numbers and percentages of patients experiencing a medication with that term. If a patient reports the occurrence of a particular medication more than once, the medication is only counted once. These will be summarized for the Safety analysis set.

Concomitant medication is defined as any medication with a start date prior to the date of the first dose of study treatment and continuing after the first dose of study treatment or with a start date between the dates of the first and last dose of study treatment. Any medication with a start date after the date of the last dose of study treatment will not be considered a concomitant medication.

A data listing of prior and concomitant medications will be provided.

H. ECOG Performance Status

ECOG Performance Status by visit will be summarized in a shift table for the Safety analysis set. The summary will also include shift to worst post-baseline value. Shifts to nominal time points will not include unscheduled visits; the shift to worst post-baseline value will include unscheduled visits. All ECOG scores will be presented in a data listing.

IX. Pharmacokinetic Analyses

Pharmacokinetic analysis will be performed in patients in the PK analysis set, and data will be listed for all patients in the Safety analysis set. Protocol Section 6.4 provides the PK sample collection time points.

Pharmacokinetic concentration data will be listed by patient including actual sampling times relative to dosing. Plasma concentrations will be summarized by phase, treatment (dose, schedule, single agent or combination therapy), cohort, and nominal visit. The following descriptive statistics will be presented at each nominal time point: n, arithmetic mean, standard deviation, coefficient of variation (CV%), geometric mean, geometric standard deviation, geometric CV%, median, minimum and maximum values.

X. Pharmacodynamic Analyses

Pharmacodynamic analysis will be performed in Phase 1 patients in the PD analysis set, and listed for patients in the Safety analysis set. See Protocol Section 6.5 for the PD assessment time points.

Concentration of 2-HG (including absolute change from baseline and/or percentage change from baseline) will be listed by patient and will be summarized by phase, treatment (dose, schedule, single agent or combination therapy), cohort, and nominal visit. The following descriptive statistics will be presented at each nominal time point: n, arithmetic mean, standard deviation, coefficient of variation (CV%), geometric mean, geometric standard deviation, geometric CV%, median, minimum and maximum values.

Geometric mean 2-HG concentration versus time profiles and/or geometric mean change from baseline versus time for each cohort will be presented graphically on a linear-linear and/or log-linear scale (as appropriate).

XI. Efficacy Analyses

Efficacy endpoints will be listed for all patients in the FAS, unless otherwise specified. Hematologic parameters evaluated for efficacy will be included in the laboratory listings, and listed for the Safety analysis set.

A. Efficacy Endpoints

Response assessments will be performed through evaluation of clinical findings and bone marrow/peripheral blood cell counts and morphology. Response criteria are derived from the International Working Group (IWG) response criteria for AML (Cheson et al. 2003) and MDS (Cheson et al. 2006) where applicable, and Stein et al. 2017, as outlined in the protocol section 4.3, Appendix 6 and Appendix 7.

Bone marrow for response assessment is required:

- at C2D1 if no peripheral blasts; otherwise, at C3D1, regardless of peripheral blast count;
- at least every 2 cycles (4 to 8 weeks) until morphologic complete remission (CR) is achieved, then up to every 3 cycles (for duration of response assessment) for 12 months after CR achievement, then up to every 6 cycles thereafter;
- when progressive disease is suspected;
- for Phase 2 Cohort 2 only: at C2D1, C4D1, C6D1 and every 6 cycles thereafter.

Response assessment requirements and frequency are the same for all subjects, including those that discontinue treatment due to hematopoietic stem cell transplant (HSCT).

In general, HSCT is not considered an event in time to event analyses. Patients who stop treatment with FT-2102 to have HSCT will continue to be monitored for duration of

response. HSCT is not considered an anti-leukemia therapy for purposes of analyses described herein.

In general, for the purposes of statistical analyses, relapse, progressive disease (PD), or disease progression will be treated interchangeably as being indicative of disease worsening.

AML Response: Following responses for AML will be evaluated by investigator based on the modified Cheson criteria (Cheson et al. 2003). Best overall response for each patient is selected based on the highest category achieved on study from the ordered list in the table below:

		Complete	Overall
Investigator Assessment of AML Response	CR/CRh	Response	Response
Molecular CR (CRm)		$\overline{\mathbf{v}}$	$\overline{\mathbf{v}}$
Cytogenetic CR (CRc)			
Complete Remission (CR)			
CR with Partial Hematologic Recovery (CRh)			
CR with incomplete recovery (CRi)			
Morphologic leukemia-free state (MLFS)			
Partial Remission (PR)			
Clinical Benefit			
Stable Disease			
Resistant Disease			
Relapse			
Progressive Disease (PD)			
Not Evaluable			
Not Done			

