The primary efficacy endpoint for all Phase 2 cohorts except for Cohort 2 is the complete response rate (CR + CRh), which will be tabulated by study phase, cohort, and dose based on the best overall response. Phase 2 Cohort 1 will test the complete response rate using a 1-sided exact binomial test for one proportion, with a 2.5% significance level. Other Phase 2 cohorts have different hypothesis tests, further described in Section 9.2.2. Additionally, the ORR will be calculated for each cohort, presented with the corresponding 95% confidence intervals, based on exact binomial methods. Number and percentage of patients within other response categories will also be presented by dose/dosing schedule and visit.

The primary efficacy endpoint for Phase 2 Cohort 2 is 4-month RFS, further described in Section 9.2.4.3.

Analyses of DOR, TTR, EFS, RFS, and OS will be based on Kaplan-Meier methods for each cohort; the median time will be tabulated along with the 95% confidence intervals.

Safety Analyses:

All safety analyses will be descriptive in nature and based on the Safety Set.

Number of DLTs, based on the DLT-Evaluable Set, will be summarized by dose level.

Safety data, including adverse events, safety laboratory values, vital signs, physical examination findings, and ECG results, will be based on the Safety Set, summarized by study stage and phase and by dose, and listed in the individual data listings as appropriate.

For selected safety parameters, National Cancer Institute Common Terminology Criteria for Adverse Events (MedDRA version 19.1) grades and the corresponding shift from baseline grade may be evaluated, based on the Safety Set, if available data permit.

Additional efficacy and safety analyses will be specified in the Statistical Analysis Plan.

TABLE OF CONTENTS

LI	ST OF TA	ABLES	23
LI	ST OF FI	GURES	23
LI	ST OF A	PPENDICES	23
AI	BREVIA	ATIONS	24
1	BACKO	ROUND	27
	1.1 I	Pharmacology	27
	1.2	Toxicokinetics	27
	1.3 I	Enzyme-Mediated Drug-Drug Interaction Potential	28
	1.4	Toxicology	28
	1.5	Clinical Rationale	29
	1.5.1	Recommended Phase 2 Dose Selection and Rationale	30
2	STUDY	OBJECTIVES	31
3	STUDY	ENDPOINTS	32
4	STUDY	DESIGN	33
	4.1 I	Phase 1 Dose-Escalation Stage	35
	4.1.1	Single-Agent (SA) Dose Escalation (Complete)	35
	4.1.2	FT-2102 + Azacitidine (Combination) Dose-Escalation (Complete)	36
	4.1.3	Definition of Dose-Limiting Toxicity	38
	4.1.4	Phase 1 Dose-Expansion Stage	38
	4.2 I	Phase 2 Stage	39
	4.3 I	Response Assessment	40

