4.1.3 Definition of Dose-Limiting Toxicity

A dose-limiting toxicity (DLT) is defined as any AE occurring in Cycle 1 that fulfills one or more of the following criteria. Toxicities will be graded and documented according to the NCI CTCAE, version 4.03 guidelines (see Appendix 4):

- Nonhematological Grade 3 or greater toxicity that is unrelated to underlying disease, occurring in Cycle 1 with the following exceptions:
 - Alopecia
 - o Grade 3 nausea, vomiting, diarrhea or rash lasting less than 72 hours (with optimal medical management)
 - o Grade 3 QTcF prolongation that is < 40 msec increase over baseline in a patient with a bundle branch block (BBB)
 - Grade 3 or 4 toxicity determined to be a sign or symptom of differentiation syndrome that resolves/responds to treatment interventions to < Grade 3 within 7 days (see Section 5.5.1)
- Any Grade 3 non-hematologic laboratory finding, unrelated to underlying disease, occurring in Cycle 1
- Hematologic Grade 4 toxicity as defined by CTCAE on Day 42, in the absence of disease
- Inability to tolerate a minimum of 75% of FT-2102 scheduled doses during Cycle 1 due to an AE. This applies to patients who have their dose held due to AEs per Section 6.8.1.

All patients will be monitored for bone marrow function throughout the study, but these findings may not be considered a DLT unless they fulfill the above criteria.

A DLT is defined within the 28 days of Cycle 1. However, the sponsor will evaluate all safety data, on an ongoing basis, beyond Cycle 1 for determination of an appropriate dose for Phase 2 or later trials.

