4.6 Replacement of Dropouts in Phase 1 Dose-Escalation Cohorts

Patients participating in Phase 1 dose-escalation cohorts who discontinue early before completing Cycle 1 for any reason other than an AE may not be evaluable and therefore may be replaced at the discretion of the Sponsor. To be considered evaluable, patients must have

completed a minimum of 75% of FT-2102 scheduled doses during Cycle 1, except those experiencing a DLT. All patients who come off study should complete both an end-of-study and a 28-day follow-up evaluation.

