9.2.3 Analysis Sets

DLT-Evaluable Set will include all patients in dose escalation who have received at least one dose of FT-2102 and completed at least 75% of doses in the first cycle during the DLT evaluation period, or have discontinued due to adverse events meeting the DLT evaluation criteria. This set will be used for DLT analyses only, unless otherwise specified.

Safety Analysis Set will include all patients who have received at least one dose of study drug (FT-2102, azacitidine, or cytarabine). All safety analyses will be based on the Safety Set unless otherwise specified. Patients will be analyzed under the first dose level received by the patient.

Full Analysis Set (FAS) will include all patients who were enrolled in the study and received at least one dose of FT-2102. This analysis set will be used for efficacy analyses. Patients will be analyzed under the assigned dose.

Efficacy Evaluable (EE) Set will include all patients in Phase 2 Cohort 1 with confirmed IDH1-R132 (by central lab) who have received the first dose of FT-2102 at least 6 months prior to the analysis cutoff date or who have died, progressed, or discontinued study participation. This analysis set is the primary set for the Phase 2, Cohort 1 efficacy evaluation. Patients will be analyzed by assigned dose.

Per Protocol (PP) Analysis Set is a subset of patients in the EE set, excluding patients who have protocol violations that could impact the evaluation of the efficacy of FT-2102. Some violations that would result in exclusion from the PP Analysis Set are: not meeting all inclusion/exclusion criteria for a particular cohort, having received chemotherapy not per protocol, received starting dose of FT-2102 other than 150 mg BID, not having at least one post-baseline response assessment. The full list of protocol violations will be reviewed on a de-identified basis by the medical, data management, and statistical leads prior to locking the database, and membership in the PP Analysis Set will be documented and determined based on that review.

PK Analysis Set consists of patients for whom it is possible to calculate at least one primary PK parameter (e.g. C_{max}, AUC_{last} and AUC_{inf}) and who do not have any major protocol deviations thought to influence the absorption, distribution, metabolism and excretion of the FT-2102.

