9.2.4.2 Safety Analysis

For DLT-evaluable patients, the summary of DLTs will be provided by dose/dosing schedule for patients in the Phase 1 dose-escalation stage. All other safety analyses will be based on the Safety Set.

For each stage, the safety and tolerability of FT-2102 will be assessed, as evaluated by adverse events, concomitant medication usage, changes from baseline in physical examination, vital signs, clinical laboratory evaluations, and ECG. Safety data will be listed by patient and summarized descriptively.

A treatment-emergent adverse event (TEAE) is defined as an adverse event with onset on or after the start of study drug, or any worsening of a pre-existing medical condition/adverse event with onset on or after the start of study drug and until 28 days after the last dose. For each stage, all adverse events will be coded using MedDRA version 19.1 or higher and summarized by SOC and PT, for each treatment group. Multiple occurrences of an AE are counted only once per patient per SOC and PT for summary tables. Causality of TEAEs (not related, related) and severity (NCI CTCAE version 4.03 or higher) will be summarized by treatment for each stage.

Relationship will be presented by study drug when applicable. All adverse events and serious adverse events (including those with onset or worsening before the start of study drug) will be listed.

Safety laboratory, vital sign, ECG and physical examinations will be summarized by visit. The change from baseline will be presented along with the by-visit summaries. Shifts in laboratory grades, as well as QTcF shifts, will be tabulated. Assessment of changes in liver function tests will be conducted. Abnormal safety assessments will be flagged and separately presented. All safety data will be listed.

Assessment of differentiation syndrome will be conducted as per Montesinos et al. 2009, searching for candidate cases of differentiation syndrome based on AE reports of dyspnea, pulmonary infiltrates, edema, weight gain, pleural effusion, renal failure, hypotension, pericardial effusion, and unexplained fever. Specific methods of identifying candidate cases will be fully described in the Statistical Analysis Plan (SAP).

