- Food Effect Cohort
 - 1. 100 mg QD
- Combination Dose with Azacitidine
 - 1. FT-2102 150 mg QD and Azacitidine 75 mg/m² I.V. or S.C. for 7 days per cycle
 - 2. FT-2102 150 mg BID and Azacitidine 75 mg/m² I.V. or S.C. for 7 days per cycle
- Combination Dose with Cytarabine
 - 1. FT-2102 150 mg BID and Cytarabine 20 mg BID S.C. for 10 days per cycle

As of Protocol Amendment 3, FT-2102 150 mg BID as SA and in combination with azacitidine will be evaluated in the proposed Phase 2 cohorts. As of Protocol Amendment 5, one patient was enrolled to receive Combination Dose with Cytarabine, after which the cohort was closed. This patient will not be summarized in tables; his data will be contained in listings only.

VI. General Analytical Considerations

A. Definition of Baseline

Unless otherwise specified, the baseline value for each quantity being analyzed is defined as the last non-missing value prior to first dose of study drug. Baseline for ECG parameter is defined as the average of the last three ECG measurements taken prior to first dose of study treatment.

For laboratory data, if a sample was taken on C1D1 that will serve as baseline, even if time of sample draw or time of dosing does not allow for a definitive determination of whether it was drawn prior to first dose.

B. Methods of Pooling Data

Data from all sites will be pooled for tabular summaries. Study center or treatment-by-center interactions will not be included in any statistical analysis. For patients enrolled in Phase 1

of the study, data from multiple dose levels from the dose escalation phase will be pooled together. Dose escalation and dose expansion phase data will be pooled together. See Appendix 3 for the table shell headers.

Phase 2 is comprised of 8 separate cohorts representing different patient populations and so patients enrolled in Phase 2 will be summarized by the cohort in which they are enrolled, and any statistical hypothesis testing will be performed within a cohort.

A single patient enrolled in the Phase 1 treatment arm of FT-2102 + low-dose cytarabine (LDAC) before that arm was closed (removed in the most recent protocol amendment). That patient's data will not be summarized; it will be listed.

C. Missing Data/ Data Imputation

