Treatment-related TEAEs leading to death	Х			
TEAE of Special Interest	X			

All AEs occurring on study (treatment emergent or not) will be provided in patient data listings. The following additional by-patient listings of AEs (treatment emergent or not) will be provided: all SAEs, all AEs leading to withdrawal of study drug, all AEs leading to dose modification, and all AEs leading to death.

In addition, a listing of all deaths with related information regarding the death will be provided, including AEs leading to death, as well as deaths that are not reported as due to an adverse event.

A summary of DLTs by system organ class and preferred term, and a listing of all AEs that caused a DLT, will be provided for the DLT evaluable set.

Adverse Events of Special Interest (AESI): Hepatotoxic and Gallbladder disorder

Some patients taking FT-2102 have experienced transaminase elevations. As such, summary tables of AEs for hepatotoxicand gallbladder disorders will be created, with tabulations of the number of patients experiencing such events by SOC and PT. Under each PT within each grouping, the time to onset will be summarized descriptively, and time to resolution will be summarized using Kaplan-Meier (KM) methods.

In addition, overall summary table for TEAEs for each AESI group will be created. It will include the number of patients with TEAEs, treatment-related TEAEs, grade 3 or 4 TEAEs, treatment related grade 3 or 4 TEAEs, serious TEAEs, treatment related serious, TEAEs resulting in FT-2102 discontinuation, treatment related TEAEs resulting in FT-2102 discontinuation; TEAEs leading to dose reduction, TEAEs leading to dose hold, treatment related TEAEs resulting in on-treatment death, treatment related TEAEs resulting in death.

All TEAEs in each group occurring on study will be provided in corresponding patient data listings.

The table below presents preferred terms in each subgroup:

Hepatotoxicity Grouping	Gallbladder disorder Grouping
Alanine aminotransferase increased	Biliary tract disorder
Aspartate aminotransferase increased	Biliary colic
Hypertransaminasemia	
Liver function test abnormal	Cholangitis
Liver function test increased	Cholestasis
Transaminases increased	
Blood alkaline phosphatase increased	
Hyperbilirubinemia	
Blood bilirubin increased	

AESI: Differentiation Syndrome

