Appendix 3 Column Headings for Analysis Tables

1. Data snapshots taken for the purpose of safety analysis (regulatory reporting, IB update, etc.) will be organized as follows:

Note: to be performed on data from both phase 1 and phase 2 patients, regardless of cohort #

2. Table generation for interim futility and efficacy analyses as well as final analyses will be organized as follows:

Phase 1:

Table xxx: Title xxx Analysis Set, Phase 1

	Single Agent		Combination: Azaci	Combination: Azacitidine 75 mg/m ² $$		
	FT-2102	Total	FT-2102	Total	Phase 1	
Parameter	150 mg BID	FT-2102	150 mg BID	FT-2102	Overall	

For Safety Tables:

Phase 2 Single Agent Therapy:

Table xxx: Title xxx Analysis Set, Phase 2 Single Agent

			FT-	-2102 150 mg H	BID	
					Phase 2	
					Single Agent	Ph.1 AML R/R
Parameter	Cohort 1	Cohort 2	Cohort 3	Cohort 7	Overall	& Ph.2 Cohort 1

Phase 2 Combination Therapy:

Table xxx: Title xxx Analysis Set, Phase 2 Combination Therapy

		FT-2102 150	mg BID + Azacitid	ine 75 mg/m²	
					Phase 2 Combination Therapy
Parameter	Cohort 4	Cohort 5	Cohort 6	Cohort 8	Overall

For Efficacy Tables:

Phase 2 Single Agent:

Table xxx: Title xxx Analysis Set, Phase 2 Single Agent

	FT-2102 150 mg BID				
Parameter	Cohort 1	Cohort 2	Cohort 3	Cohort 7	Ph.1 AML R/R & Ph.2 Cohort 1

Phase 2 Combination Therapy:

Table xxx: Title xxx Analysis Set, Phase 2 Combination Therapy

FT-2102 150 mg BID + Azacitidine 75 mg/m²

Parameter	Cohort 4	Cohort 5	Cohort 6	Cohort 8

DocuSign

Timestamp

Certified Delivery Events

Status

Carbon Copy Events	Status	Timestamp	
Witness Events	Signature	Timestamp	
Notary Events	Signature	Timestamp	
Envelope Summary Events	Status	Timestamps	
Envelope Sent	Hashed/Encrypted	2/19/2023 7:01:45 PM	
Certified Delivered	Security Checked	2/20/2023 3:01:41 PM	
Signing Complete	Security Checked	2/20/2023 3:02:20 PM	
Completed	Security Checked	2/20/2023 3:02:20 PM	
Payment Events	Status	Timestamps	
Electronic Record and Signature Disclosure			

CONSUMER DISCLOSURE

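### The SAP's Phase 1 tables pool dose levels, so the by-dose DLT and safety summaries required by the protocol are missing for the three single-agent QD levels

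*SAP*

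**What the plan says.** **Protocol.** The synopsis (Safety Analyses) states: "Number of DLTs, based on the DLT-Evaluable Set, will be summarized by dose level". Section 9.2.4.2 repeats the commitment: "the summary of DLTs will be provided by dose/dosing schedule", for patients in the escalation stage. The synopsis also asks for the remaining safety data to be broken down by stage, phase and dose.

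**SAP.** Section VI.B says of Phase 1 that "data from multiple dose levels from the dose escalation phase will be pooled together", then pools escalation with expansion and refers to Appendix 3 for the table headers. Section VI.I sends the summary tables for the analysis sets, which include the DLT Evaluable Set, to the Appendix 3 layout. Appendix 3 introduces that layout with "Table generation for interim futility and efficacy analyses as well as final analyses will be organized as follows". Its Phase 1 shell has 150 mg BID and Total under single agent, the same two under the azacitidine combination, and one overall column. Section VIII.B plans "A summary of DLTs by system organ class and preferred term", together with a listing of the AEs that caused a DLT. It names no split by dose.

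**DLT-Evaluable Set.** Protocol 9.2.3 admits patients who completed at least 75% of Cycle 1 doses, "or have discontinued due to adverse events meeting the DLT evaluation criteria". The protocol synopsis and SAP VI.I add interruption as a further route into the set. Protocol 4.6 applies the 75% requirement to everyone "except those experiencing a DLT".

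**The concern.** The Phase 1 primary objective is to determine DLTs, the MTD or MED, and the Phase 2 dose. The primary endpoint is the incidence and severity of AEs, laboratory abnormalities and ECG changes. These are questions about each dose and schedule. The protocol defines the MTD from the number of patients with a DLT at a single level, so a reader of the final report needs, for each level, how many patients were evaluable and how many had a DLT.

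Under the SAP's layout the tables do not show this for the single-agent QD levels, and the AE profile at 150 mg BID cannot be set beside the profile at each alternative. The SAP gives no reason for departing from the protocol. By-dose tables are evidently practicable, because SAP IX and X summarize plasma concentrations and 2-HG by dose and schedule.

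**Working it through.** The plan states no figure on this point, so the check is a comparison of texts followed by a labelled illustration.

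**1. Regimens against columns.** SAP V.A lists six Phase 1 regimens besides cytarabine, whose single patient is to be listed only.

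| Regimen | Own column in the Phase 1 shell | DLT/TEAE rate recoverable from the tables |
|---|---|---|
| 150 mg QD | no | no |
| 300 mg QD | no | no |
| 100 mg QD, food-effect cohort | no | no |
| 150 mg BID | yes | yes |
| 150 mg QD + azacitidine | no | yes, combination Total minus 150 mg BID |
| 150 mg BID + azacitidine | yes | yes |

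The subtraction in the fifth row assumes that only the two listed combination levels were given. For single agent, Total minus 150 mg BID gives one sum over three levels: one equation with three unknowns.

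The other layout in Appendix 3, for safety snapshots, has no QD column either. The TEAE table by grade is coarser still: SAP VIII.B gives it for Phase 1 only as a single-agent total and a combination total.

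**2. Stage.** The 150 mg BID columns also mix escalation and expansion patients for TEAEs. They do not for DLTs, because the DLT Evaluable Set is restricted to escalation.

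**3. Illustration.** The documents do not give the evaluable number or the DLTs per level. Assume 6, 6 and 6 evaluable patients at 150 mg QD, 300 mg QD and 150 mg BID, 3 in the food-effect cohort, and two DLTs, both outside 150 mg BID.

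- Shown in the table: 150 mg BID 0/6; Total 2/(6+6+6+3) = 2/21 = 9.5%.
- By subtraction: 2/(21−6) = 2/15 = 13.3% for the three QD levels together.
- Patterns that give exactly this table, in the order 150 mg QD, 300 mg QD, 100 mg QD with food:
  - 2/6, 0/6, 0/3 (33.3% at one level)
  - 1/6, 1/6, 0/3 (16.7% at two levels)
  - 0/6, 0/6, 2/3 (66.7% at one level)

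The first and third patterns have two DLTs at one level, which is the stopping condition in protocol 4.1.1; the second does not. The table cannot tell them apart.

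Range over cohort size, keeping 6 at 150 mg BID and both DLTs at one QD level:

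- three patients at each QD level: 2/3 = 66.7% at the level, and 2/(6+3+3+3) = 2/15 = 13.3% in Total
- six patients at each QD level: 2/6 = 33.3% at the level, and 2/(6+6+6+6) = 2/24 = 8.3% in Total

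**4. DLT-Evaluable Set.** Take a patient whose FT-2102 is held for an AE, who falls below 75% of Cycle 1 doses and then resumes.

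- Protocol 4.1.3 counts this as a DLT: "Inability to tolerate a minimum of 75% of FT-2102 scheduled doses during Cycle 1 due to an AE". It says expressly that held doses are covered.
- Protocol 4.6: evaluable, through the exception for patients with a DLT.
- Protocol synopsis and SAP VI.I: in the set, through interruption.
- Protocol 9.2.3: below 75% and not discontinued, so neither route applies.

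Section 9.2.3 therefore conflicts with the other three definitions. SAP I says that the SAP governs the analysis, so the patient stays in both numerator and denominator.

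**The case against.** The best reply is that little information is lost. 150 mg BID, the dose taken forward, has its own column with and without azacitidine, and the other combination level follows by subtraction. SAP VI.K orders listings by dose and schedule, and a listing of every AE that caused a DLT is planned. Since VI.K also calls for derived variables to be listed, evaluability may be visible patient by patient. All of this stands, and it rules out saying that DLTs are not reported by dose at all. It does not meet the protocol's commitment, which is to a summary. A reader would have to rebuild numerators and denominators by hand for three levels.

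The SAP says it is based on protocol version 5, so that text may have differed. The by-dose requirement is nevertheless in the current protocol, and the SAP records no reason to drop it.

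A reader might infer that the choice of dose is undermined because the MTD rule rests on these tables. The documents do not support that. Under protocol 4.1.1, escalation was decided level by level, with AE review before each new level opened. The single-agent and azacitidine escalations are marked complete, and protocol 1.5.1 records that the Phase 2 dose was declared after sponsor safety reviews in 2018.

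A reader might also infer from 9.2.3 that DLT rates will be biased downward, or that a failing level could seem to pass. Neither follows. The SAP definition keeps held-dose DLTs in the set, and passing after a first DLT requires five of six patients to complete the cycle without one.

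**Conclusion.** The mismatch between protocol and SAP is real and should be corrected. The protocol promises DLT summaries by dose level and schedule and safety summaries by dose; the SAP's tables omit them for three of the six non-cytarabine regimens, all single-agent QD levels. The consequence is incomplete final reporting of the Phase 1 primary objective. No sample size, error rate or escalation decision changes.

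The 8.3% to 13.3% totals in the illustration rest on assumed cohort sizes and assumed DLTs. They show how far a pooled figure can sit from a level's own rate, and are not evidence that any level failed.

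The DLT-Evaluable Set conflict is secondary: a wording inconsistency within the protocol that does not affect the analysis as the SAP defines it.

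**What to change.** In SAP VI.B and Appendix 3, exempt the DLT table and the main Phase 1 TEAE summary from pooling. Give one column for each dose and schedule actually given, four single-agent and two with azacitidine on the SAP's own list. Each column should show the DLT-evaluable number, the number with a DLT and the TEAE summary. Keep the pooled columns as supplementary. If escalation and expansion remain combined for TEAEs, say so and give the reason, since the protocol synopsis asks for a split by stage as well.

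The cost is a wording change and two reprogrammed tables, some with small columns. The SAP's rule against summaries of fewer than five patients is stated for by-visit data such as laboratory, vital sign and ECG results, not for AE tables, so it is no obstacle.

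As a separate consistency edit, reconcile the DLT-Evaluable Set in protocol 9.2.3 with the synopsis, SAP VI.I and protocol 4.6, so that one definition stands throughout. That is one clause.
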